1. BACKGROUND AND SIGNIFICANCE

Sickle cell disease (SCD) is an autosomal recessive disorder that affects 1 of every 400 African-American newborns in the United States.^{42,43} Abnormal hemoglobin, due to a mutation in the sixth codon of the β -globin gene, is the basis for SCD.⁴⁴ Under hypoxic conditions, the abnormal hemoglobin polymerizes, causing red blood cells to become sickle-shaped and unable to transverse the microvasculature.⁴⁴ Occlusion of small vessels results in tissue ischemia, infarcts and organ damage.^{44,45} Commonly affected organs include the brain, lungs and bone, which result in stroke, acute chest syndrome and pain, respectively.⁴⁵ Red cell transfusion is the most critical therapy to treat and prevent complications of SCD.¹

Adults with SCD depend on red cell transfusion to prevent stroke and critical illness. Red cell transfusion corrects anemia, decreases sickle hemoglobin (HbS) percent, suppresses HbS synthesis, and reduces red cell hemolysis.^{1,44,45} These beneficial effects are used to successfully manage multiple complications from SCD, including severe anemia, stroke, acute chest syndrome and multi-organ failure.^{1,44-55} When administered on a chronic basis, typically monthly, transfusion decreases rate of cerebral infarcts by up to 45%⁵¹ and vaso-occlusive events by up to 50%.⁵³⁻⁵⁷ Other than transfusion, hydroxyurea is the only medication available for SCD.^{1,58} Although hydroxyurea decreases rate of vaso-occlusion and prolongs life, the drug is not indicated for stroke prevention and is ineffective in 50% of patients.⁵⁹⁻⁶⁴ Since red cell transfusion remains the cornerstone of therapy for this population, provision of the safest units possible is critical.

Changes occur in the physiology of red cell units with prolonged storage that may trigger a cascade of deleterious events in the transfusion recipient: macrophage activation, inflammation and release of toxic iron species (Figure 1). Red cells preserved with Adsol solution can be stored up to 42 days,⁶⁵ a recommendation based on integrity, not red cell efficacy or safety. Significant oxidative and metabolic changes occur with storage: hemolysis with release of cell-free hemoglobin, heme, and non-transferrin bound iron (NTBI), as well as alterations to the lipid composition of the red cell membrane.⁶⁻¹⁵ Surface exposure of phosphatidylserine (PS), a phospholipid normally found on the inner leaflet of the red cell membrane but which becomes externally exposed with storage, may be the most important of these changes.²³⁻²⁷ Macrophages recognize PS as an “eat me” signal via specific receptors (Tim1, Tim4, and Stabilin-2) and rapidly phagocytize these red cells.⁶⁶⁻⁷¹ In pre-clinical studies, phagocytosis of old red cells results in activation and secretion of pro-inflammatory cytokines, such as IL-1, IL-6, IL-8, CXCL-1 and monocyte chemoattractant protein-1 (MCP-1).^{19,28} Phagocytosis of a bolus of old red cells also overwhelm the macrophage’s metabolic capacity, leading them to release cell-free hemoglobin, heme and NTBI with downstream effects.^{21,22,29-31} NTBI has been associated with fatal proliferation of ferrophilic bacteria and the generation of toxic reactive oxygen species.^{19-22,37-39} Of note, these effects on macrophages are only seen after the transfusion of older intact red cells, not from the products of lysed red cells, which suggests that phagocytosis of red cells is required to generate this pathophysiology.²⁹

Although some patients may be able to tolerate the aberrant physiology of older red cells, others may be at risk of poor outcomes.

Adults with SCD may be uniquely susceptible to the deranged physiology of older units because they are prone to infections, inflamed and poorly equipped to handle excess red cells with high PS. Vaso-occlusion-induced tissue damage activates macrophages and leukocytes, which in turn leads to a chronic pro-inflammatory state.⁷²⁻⁷⁶ Reperfusion injury further exacerbates inflammation with the generation of reactive oxygen species as well as additional endothelial and leukocyte activation.^{77,78} Activated macrophages, leukocytes and endothelium then promote more vaso-occlusion in what becomes a vicious cycle of ischemia, injury and inflammation.⁷⁸ Intravascular hemolysis with release of cell-free hemoglobin and heme also contributes to this pathophysiology as cell-free hemoglobin is a sink for nitric oxide, a potent vasodilator and platelet antagonist,^{32-34,78} and heme activates endothelial cells via TLR4 receptors.^{35,36} Prior to penicillin prophylaxis, infection was the primary cause of death in patients with SCD due to splenic dysfunction.⁷⁹⁻⁸¹ The cumulative result of SCD's pathology is an adult who is prone to infections, chronically inflamed and susceptible to the pathology of PS-high, older red cells, and the consequent increased levels of cell-free hemoglobin, heme and NTBI in circulation. In fact, on sickle erythrocytes (not transfused cells) PS exposure is well-known to cause adhesion to the endothelium and thrombin generation, both of which worsen the pathology of vaso-occlusion.^{82,83} Since older red cell units with increased PS exposure can promote a similar physiology as SCD, they may exacerbate the illness of these vulnerable patients.

No prospective study has evaluated the effects of an older unit with high PS exposure in an adult with SCD. There has only been one recently published prospective study in patients with SCD to examine the effects of age of blood.⁸⁴ This was a randomized trial, conducted in Africa, of young children with either SCD or malaria transfused with > 25 day-old units versus < 10 day-old units to treat severe anemia (mean Hgb 3.7g/dl) with evidence of lactic acidosis. Although the trial found no difference between the two arms in the primary outcome measure, blood lactate levels, the results do not address the question of the current proposal: do PS-high, older units trigger a pathobiology in chronically transfused adults with SCD that leads to infection? Differences in unit physiology, patient inflammation, infection rates, and pain were not examined in the prior study, which is why the current study needs to be conducted. Other than that one prospective study, the only data about the effects of older units in SCD comes from three observational cohort studies, all of which showed an adverse outcome (increased red cell alloimmunization and decreased vascular dilatation) associated with older units.⁸⁵⁻⁸⁷

The effects of the older units have been equally inconsistent in other patient populations, mostly trauma and surgery. While multiple observational studies have associated receipt of old units with poor outcomes, including infection and death,⁸⁸⁻⁹⁰ recent randomized prospective studies did not show a difference in mortality.^{91,92} Limitations of these other previous studies were a small difference in age between older and younger units, as well as the fact that no evaluation was performed of the unit's

physiology. Not all older units show the same degree of pathology.⁶⁶ Most pertinent to our study, however, is that the patients were not adults with SCD. Organ dysfunction, inflammation, hemolysis, along with a dependence on blood to prevent critical illnesses, creates a situation in adults with SCD that is different from other patient populations, including children with SCD, and makes studies in other populations difficult to apply. To address a critical gap in knowledge, **we propose for the first time, a prospective, randomized study to elucidate the immunological and clinical effects of an older unit with high PS exposure on adults with SCD.**

Preliminary Studies

In Milwaukee, 1/3 of units transfused to adults with SCD are >30 days old, but nation-wide some restrict the transfusion of older units. Four hundred adults receive care in the Adult Sickle Cell Clinic at UNC in Chapel Hill, 47 of who receive chronic outpatient transfusions for chronic pain or stroke prophylaxis. Transfusions are administered to adults regardless of storage age. In a 3-year retrospective review of transfusions administered to adults with SCD, 896 units were transfused over 407 simple transfusion encounters. Median storage age was 23 days (range: 2-42 days); 32% of units provided were \geq 30 days-old (**Karafin et al., 2015**).⁴¹ To evaluate the opinions and policies of other hospital blood bank directors about the use of older red cell units for patients with SCD, we conducted a nation-wide survey (n=90). While only 23% of respondents had a storage age restriction policy for patients with SCD, 31% thought that older units were not as effective as younger units, and 65% believed that evidence-based policies were needed (**Karafin et al., 2015**).⁴⁰ These data from our institution and across the US demonstrate equipoise among blood bank directors about the potential harm of older units for patients with SCD. At UNC, we have determined that the average unit age transfused is 18 days, with a standard deviation of 10 days (range: 5 days- 39 days).

Transfusion of older units to adults with SCD stimulates expansion and activation of macrophages. Adults with SCD may be susceptible to the effects of an older unit's physiology because they are prone to infection, chronically inflamed, and poorly equipped to handle excess iron. In a cohort of 40 steady-state adults with SCD, we specifically measured markers of inflammation and iron excess. High sensitivity C-reactive protein, a marker of global inflammation, was found to be markedly elevated (median 5.6 mg/L, range 0.4-60 mg/L; reference range <1.0 mg/L), as was ferritin, a marker of iron stores (median 2,969 ng/ml, range 20-12,300 ng/ml; reference range 13-400 ng/ml) (**Karafin et al., 2015**).⁹³

To characterize whether older units would exacerbate the adult's pro-inflammatory physiology, we next examined activation of macrophages, neutrophils, B and T cells in the peripheral blood of 8 adults with SCD before and after transfusion and 8 adults with SCD who do not receive transfusion (ages 19-35). All transfused units were greater than 14 days old (range, 14-36 days). In support of our hypothesis, we identified that absolute macrophage and neutrophil numbers were higher post-transfusion compared to pre transfusion in 5/8 (63%) and 6/8 (75%) subjects, respectively. There was also evidence of macrophage activation post-transfusion (**Figure 2**). Among transfused subjects,

macrophages increased in size in 7/8 (88%) subjects, and showed greater expression of CD64+ (12% increase) and CD62L (34% increase) as measured by mean fluorescence intensity (MFI) 24 hrs post-transfusion as compared to pre-transfusion values.

[figure not shown]

Figure 2: CD64 macrophage activation at time 0 and 24 hours in adults with SCD not transfused (**A**), transfused (**B**) and a comparison between not transfused and transfused (**C**). Macrophages were identified by CD14 expression (rectangles on scatter plots in (A) and (B)), and further analyzed for activation by CD64 expression (histograms gray=time 0, red=24 hours). There is a trend suggesting transfused subjects have a greater increase in CD64+ macrophages 24 hrs post transfusion.

Transfusion of older red cell units to adults with SCD increases rate of infection. To explore whether the pro-inflammatory state stimulated by older units was associated with infection risk, as has been shown in pre-clinical models, we examined 29 adults with SCD who were treated with a chronic transfusion program. A random effects model, which accounts for a subject's contribution to repeat encounters, was used to define the association between infection and storage age. This model revealed that a mean unit age > 25 days old was associated with a significant increase in ED or hospital admissions for infection ($p=0.03$). After receipt of older units, adults developed pneumonia ($n=6$), urinary tract/kidney infections ($n=2$), gynecologic infections ($n=2$), an ear infection ($n=1$), a wound infection ($n=1$), and sepsis ($n=1$). Eight (62%) of these infections contributed to a subsequent inpatient admission (**Karafin et al., submitted for publication**).

Our preliminary data demonstrates the need for a prospective, randomized trial to characterize the effects of an older unit's physiology on adults with SCD. Because little data exist, blood bank directors across the country have varied policies about the provision of older units to adults with SCD. At our institution, adults are frequently transfused with older units, which we have shown activate macrophages and, ultimately, promote infection.

Summary: Finding ways to maximize the safety and efficacy of red cell transfusion therapy for patients with SCD is desperately needed. Our group has data suggesting that older units of stored red cells contribute to immune activation and the increased risk of infection. If found to be effective, restricting transfusions to PS-low, younger units of blood in this population has the potential to improve patient outcomes and significantly alter the field of transfusion medicine.

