- 3) Current participation in another therapeutic trial for sickle cell disease
- 4) Current pregnancy
- 5) History of HIV infection
- 6) Having an uncontrolled inter-current illness, or psychiatric illness/social situations that would limit compliance with study requirements as determined by the principal investigator.

Study procedures:

Red cell unit preparation: Red cell units for transfusion will be crossmatch-compatible, sickle-negative, and phenotype-matched for D, C, E, and K red cell antigens per current hospital protocols. Red cell unit age will be documented by the blood bank at the time of randomization. Study transfusions will take place *only* in the outpatient infusion clinic.

Pain and infection diary: The diary is adapted from a model widely used in SCD studies. Daily, participants will rate pain on a numeric ordinal pain rating scale (0-10), indicate whether the pain was consistent with a “crisis,” indicate whether they utilized a healthcare facility, and record the amount of opioids used. Infection symptoms will also be documented daily along with the type, duration, and dose of antibiotics, if applicable.

Physical exam: A basic, focused, physical exam will be performed on each subject by the PI or trained delegate prior or during each transfusion and prior to the completion of the study. The physical exam will assess a general review of systems, a review of the pre-transfusion vital signs, and a basic evaluation of patient general status, heart, lung,

and neurological organ systems. We will also document if the patient has an indwelling catheter.

Blood measurements:

Unit samples: Red cell characteristics: 2 ml blood from each red cell unit will be obtained from 6 sterile unit links pre-transfusion. RBC PE and PS surface exposure, and plasma microparticles will be quantified by flow cytometry using the LSR2-green, and all flow analyses will be recorded using FACSDiVa software. The plasma fraction from each unit sample will be diverted to EPR (Bruker Elexys X-band system, Billerica, MA, USA), a Bio-Plex cytokine assay kit (Bio-Rad Laboratories), and a fluorescent immunoassay (DxFerr kit) to measure concentrations of free heme/hemoglobin, cytokines (IL-1, IL-6, IL-8, MCP-1), and NTBI, respectively. A small sample will also be frozen for future metabolomic analysis.

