2.2 Secondary Aims

Aim 1:

To explore whether: ≥ 30 day-old units will have significantly greater mean 1) phosphatidylethanolamine expression, 2) cell free hemoglobin concentration, 3) cell free heme expression, and/or 4) NTBI expression in comparison to ≤ 10 day-old units.

Aim 2:

To explore whether:

- 1) Those administered ≥ 30 day-old units will have a greater increase in the number of activated monocytes or neutrophils as defined by flow cytometry markers of activation at 2 or 24 hours post-transfusion compared to those administered ≤ 10 day units.
- 2) Those administered ≥ 30 day-old day units will have a greater increase in the concentration of NTBI, cell free hemoglobin, and free heme, compared to those administered ≤ 10 day-old units at 2 or 24 hours post transfusion.
- 3) Recipient RBC PS, PE, and microparticle expression will increase more between 2 and 24 hours after receiving ≥ 30 day-old units than after receiving ≤ 10 day units.

Aim 3:

To explore whether those administered ≥ 30 day-old units will have a more rapid increase in the concentration of HbS% and a more rapid decrease in hemoglobin over time compared to those administered ≤ 10 day-old units.

Aim 4:

To explore whether those administered ≥ 30 day-old units will have a significantly different RBC metabolomic profile 2 and 24 hours post transfusion than those provided ≤ 10 day-old units.

Aim 5:

We will address aspects of study feasibility, such as subject drop-out, rates of missing data, and the confidence intervals/precision of our recorded variables, including PS, PE, microparticles, CD62L, and the other recorded clinical variables.

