Patient Sample Processing: Blood will be obtained by port or peripheral access as available. Patient white cells will be isolated with established Ficoll separation techniques.. White cells will be tested by flow cytometry as above for key markers of activation (macrophages: CD62L, CD64, CD80, CD86, Tim1, neutrophils: The plasma fraction from each sample will be diverted to EPR (Bruker Elexys X-band system, Billerica, MA, USA), a Bio-Plex cytokine assay kit (Bio-Rad Laboratories), and a fluorescent immunoassay (DxFerr kit) to measure concentrations of free heme/hemoglobin, cytokines (IL-1, IL-6, IL-8, MCP-1), and NTBI, respectively. Clinical measurements obtained from patients will also include: CBC (4ml EDTA), reticulocyte count (4ml EDTA), HbS% (3ml EDTA), haptoglobin (1ml red top), chemistry labs (ferritin (0.5ml red top), iron saturation (1ml red top), lactate dehydrogenase (1ml red top)), urinalysis (12 ml) and blood culture (8-10ml/bottle). These clinical labs will be measured at intervals specifically defined in **Table 1**. Individual human samples of plasma and RBC will also be sent to [name] at the University of Colorado Denver to measure lipid metabolites and metabolomic profiles pre vs. post transfusion as an additional exploratory goal of this trial. The laboratory of [name] and his representatives will be receiving 30-200 individual samples of plasma and RBCs for this purpose. All samples will be de-identified.

6.3 Patient Clinical Outcomes:

A daily pain diary will be used and subjects will rate their pain on a ordinal numeric pain rating scale (0-10), indicate whether the pain was consistent with a “crisis,” indicate whether they utilized a healthcare facility, and record the amount of opioids used. Infection symptoms will also be documented daily along with the type, duration, and dose of any antibiotics taken if applicable. Subject ED and hospitalization events, and etiologies (see *definitions in 6.7*), will be recorded at regular intervals by the study coordinator during the study period using the available electronic medical record. Of note, diary completeness will be assessed at each face-to-face visit.

6.4 Patient Physical Exam:

Prior to each randomized transfusion, the PI or appropriately trained designee will perform a basic assessment of the patient. This exam will include a basic interval history (including review of any ED or hospital visits), a focused review of systems, and a focused physical exam.

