Exploratory: We will explore the relationship of blood age and transfusion of biochemically old red cell units on the change in Hb and HbS% over time, daily pain scores (0-10 as an ordinal scale), opioid use and dose, ED and hospitalization rate, infection symptoms, new alloantibody formation, and antibiotic use during the 3-month study period. We will compare groups using a Fisher exact test. We will also plan for auxiliary analyses of the outcome variables in which the explanatory variable is the age (days) of the RBC units --to characterize the degree to which age (days) can accurately predict the clinical and physiologic outcome measures defined.

AIM 4:

We will calculate the mean, median, minimum, and maximum levels of each metabolic compound analyzed by [name] in his laboratory at the University of Colorado. Analysis tools and methods will be determined by his research team, and will focus on changes in the patient and the unit pre and post transfusion.

AIM 5:

Feasibility Analysis: We will assess important variables necessary to develop a future larger clinical trial on this subject. Areas that we will investigate during the course of this trial will include frequency and content of missing data, subject drop out rates, and estimates of outcome measure precision. For this study, we will evaluate the number of males, females, and adolescents that enroll in the study to inform future studies. We do not expect there to be differences in the key outcomes based on these variables, and plan to analyze all 40 subjects together as one cohort, but differences by age and gender will be evaluated and considered.

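### Secondary Aim 3: neither Hb nor HbS% alone shows whether transfused cells are lost faster; add non-S (donor) hemoglobin, computable from the same samples, as a further analysed variable

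*Combined protocol and SAP*

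**What the plan says.** Section 2.2, Secondary Aim 3, sets out to explore whether recipients of the older units "will have a more rapid increase in the concentration of HbS% and a more rapid decrease in hemoglobin over time" than recipients of the younger units. The matching analysis is in Section 10.2.1, in the exploratory paragraph under Aim 3. It studies the effect of blood age and of biochemically old units "on the change in Hb and HbS% over time", in one list with pain scores, opioid use, admissions, alloantibodies and antibiotic use. The only between-group test named for that list is: "We will compare groups using a Fisher exact test". The same paragraph adds auxiliary analyses with unit age in days as the explanatory variable.

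Three other places matter:

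- Section 1 says of transfusion in SCD: "Red cell transfusion corrects anemia, decreases sickle hemoglobin (HbS) percent, suppresses HbS synthesis, and reduces red cell hemolysis".
- The synopsis, under red cell unit preparation, says: "Red cell units for transfusion will be crossmatch-compatible, sickle-negative, and phenotype-matched for D, C, E, and K red cell antigens".
- Table 1 marks the CBC (whose footnote includes Hgb) and HbS% at the same three times: before every transfusion, 24 hours after and 2 weeks after. Neither is marked at 2 hours or at end of study.

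No section multiplies Hb by an HbS or HbA fraction, defines donor hemoglobin, or adjusts for the patient's own HbS production.

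**The concern.** A faster rise in HbS% with a faster fall in Hb is what one would expect if older units were cleared sooner. Section 1 describes macrophages rapidly removing PS-exposing cells, so that is a natural use of the result. Each variable, however, is the net result of two processes: loss of donor cells and output of the patient's own cells. Greater own output raises HbS%, which looks like faster donor loss, and also raises Hb, which looks like slower donor loss.

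At stake is how the result can be read. Extra donor loss that the marrow replaces leaves Hb almost unchanged. A rise in HbS% can occur with no extra donor loss at all. If only one of the two variables moves, the plan gives no way to tell which process caused it. Section 2.1 says the data will inform a larger study, so the ambiguity could carry forward.

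**Working it through.** The documents give no sample size, power, SD or effect size for Secondary Aim 3, so there is no figure to reproduce. The check is algebra, followed by illustrations on assumed values.

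**Identity.** Let D be donor Hb and S the patient's own Hb, taken as all HbS for now. With sickle-negative units:

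- Hb = D + S
- HbS fraction = S / (D + S)
- therefore D = Hb x (1 - HbS fraction) and S = Hb x HbS fraction.

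Hb and HbS% each depend on both D and S. Neither identifies D alone; the product does.

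**Same loss, opposite signals.** Assume Hb 10.0 and HbS 30% at 24 h, so D = 7.0 and S = 3.0 g/dL. Two patients each lose 12% of donor cells: D = 7.0 x 0.88 = 6.16.

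- S becomes 3.3: Hb = 9.46, HbS = 3.3/9.46 = 34.9%.
- S becomes 4.3: Hb = 10.46, HbS = 4.3/10.46 = 41.1%.

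The second patient looks worse on HbS% and better on Hb. Hb x (1 - HbS fraction) returns 6.16 for both.

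**Same reading, different loss.** From the same start:

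| Donor loss | D | Own S if later HbS is 40% | Hb in that case | Own S if later Hb is 9.5 | HbS% in that case |
|---|---|---|---|---|---|
| 10% | 6.3 | 4.20 | 10.5 | 3.2 | 33.7 |
| 20% | 5.6 | 3.73 | 9.33 | 3.9 | 41.1 |
| 30% | 4.9 | 3.27 | 8.17 | 4.6 | 48.4 |

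With no donor loss and S up by 1.5 g/dL, HbS% still rises from 30% to 4.5/11.5 = 39.1%.

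**What this could mean for power.** The 20 per arm comes from Section 2.1; every other input is assumed. These are 24 h Hb 10 (SD 1), HbS 35% (SD 8), two-week donor loss 12% v 17% (SD 4 points), own Hb gain 0.5 g/dL (SD 0.4), and assay error 0.2 g/dL and 1 point. Each change is compared by a two-sided t-test at 0.05. Simulated power:

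| Share of the extra donor loss replaced by own output | Donor Hb | Hb | HbS% |
|---|---|---|---|
| None | 77% | 44% | 27% |
| Half | 76% | 15% | 66% |
| All | 75% | 5% | 92% |
| Half, with 5% plasma-volume variation | 55% | not compared | 68% |

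Donor Hb leads in the first two rows and HbS% in the last two.

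**Limit of the derived variable.** Hb x (1 - HbS fraction) counts the patient's own non-S hemoglobin as donor. For a true 15% loss while own Hb rises from 3 to 4 g/dL, an own non-S share of 10% gives (5.95 + 0.4)/(7 + 0.3) = 0.870, an apparent loss of 13.0%. Shares of 5%, 20% and 50% give 14.0%, 11.2% and 6.5%.

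**The case against.** The strongest reply is that the plan never says Secondary Aim 3 measures donor-cell loss. It names Hb and HbS% as the outcomes, and Section 1 treats correcting anemia and lowering HbS% as benefits in their own right. On that reading own output is part of the outcome and not noise. This stands: donor-cell loss is a reasonable inference from the hypothesised pattern, but still an inference. Replacing the two named outcomes would change the question asked.

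Second, the hypothesis is a joint pattern. If, from equal starting values, Hb falls more and HbS% rises more, both factors of Hb x (1 - HbS fraction) are lower, so donor Hb must have fallen more. That is valid evidence. The gap lies in cases where only one variable moves or the two disagree; the plan specifies neither a joint test nor a combined variable for them.

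Third, a reader might infer that donor Hb is the uniformly better or more stable endpoint, or that it shows loss directly. The documents do not support that. They supply none of the SDs or effect sizes, and the ranking reverses within plausible assumptions. Donor Hb is a concentration that moves with plasma volume, which HbS% does not. It includes HbF, HbA2 and any other own non-S hemoglobin (Section 4.2 does not stratify by hemoglobinopathy type). It also includes donor cells from earlier transfusions, given on the 3-8 week schedule of Section 6.8. A change measured from 24 h misses anything cleared before then, although Section 1 describes rapid phagocytosis.

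Finally, the variable could be derived after the fact from data already collected. That is true, but specifying it beforehand costs no more and avoids a choice made after seeing the results.

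**Conclusion.** The point holds in a limited form. From the sickle-negative units and the plan's own statement that HbS synthesis changes with transfusion, neither Hb nor HbS% alone can show whether transfused cells are lost faster. The two can also give opposite signals for identical loss. This follows from algebra and needs no assumed variances. Non-S hemoglobin closes the gap, up to the patient's own non-S fraction, plasma-volume shifts and carry-over of earlier donor cells.

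The size of any power gain is not established. Under the assumptions shown, donor Hb has about 75-77% power whatever the marrow response if plasma volume is stable. HbS% ranges from 27% to 92% and exceeds donor Hb in some cases. This supports adding the variable; it does not support demoting Hb or HbS%. The aim is exploratory, in a study that Section 2.1 calls a feasibility study, and no primary outcome, sample or safety decision is affected. Priority is low.

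**What to change.** In Secondary Aim 3 and the Aim 3 exploratory paragraph of Section 10.2.1:

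1. Add non-S (donor) hemoglobin, Hb x (1 - HbS fraction), or Hb x HbA fraction if HbA is reported, as an analysed variable.
2. Compare between arms its log change from 24 h to 2 weeks after each study transfusion, and from 24 h to the next pre-transfusion sample. Allow for elapsed days in the latter, because the interval varies. Table 1 marks no CBC or HbS% at end of study, so this second comparison is scheduled only after the first and second study transfusions.
3. Analyse it as a continuous repeated measure. Section 10.2 already names random effects models for repeated measures. A Fisher exact test does not suit continuous changes, and that applies equally to Hb and HbS%.
4. Keep Hb and HbS% as the stated outcomes, and say in advance how concordant and discordant results will be read.
5. Add a sensitivity analysis for own non-S hemoglobin (HbF, HbA2, other genotypes), and state that loss before 24 h, plasma-volume change and earlier donor cells are not separated.

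The cost is one derived variable and a few lines of text. No new sample or visit is needed, and no primary analysis changes.
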